**ID:** 9R44MH117956-02

**Title:** PlusCare: Mobile Platform to Increase Linkage to Care in Adolescents Living With HIV/AIDS

**NCT ID:** NCT03758066

**Date of Protocol:** 3/15/2018

**Dates Approved by Sites:** 1/2/2019 (BCH) and 2/01/2019 (BMC)

**Study Objective and Overview:** To conduct a mixed-methods, non-randomized pre-post study to test PlusCare, a mobile application, in real-world clinical settings. In a Phase I project, members of the research team demonstrated the acceptability and feasibility of PlusCare, a mobile application system developed by Dimagi, Inc. to support HIV case management for youth living with HIV (YLH) aged 13 to 25 years old. In this Phase II SBIR project, we will enhance the PlusCare system to best serve the team-based care delivery model identified in Phase I and test it in a non-randomized, pre-post intervention study conducted in multiple clinical settings. The objective of this Phase II project is to test and demonstrate the effectiveness of PlusCare on HIV case management process and care continuum outcome measures.

**Study Design:** Patients and case managers (CMs) will be recruited from three HIV case management programs in two hospitals in the metro Boston area. Patients will use the PlusCare application for 12 months, while CMs will use the system for at least 15 months in order to account for rolling patient recruitment (i.e., 3 months to enroll target number of patients). We will perform a process and outcomes evaluation of the system to determine the effect of the PlusCare intervention on HIV health status and case management outcomes.

**Patient Selection and Inclusion/Exclusion Criteria:** A research assistant (RA) will recruit CMs (N=20) and patients (N=50).

The patient eligibility criteria are as follows:

*Inclusions:*

- 1) between 13-25 years old,
- 2) patient of the BCH HAPPENS or BCH CHAP program,
- 3) HIV-positive,
- 4) own or ability to access a smartphone (e.g., iPhone, Android) for one year, and
- 5) be in care for at least 1 year prior (for access to historical control data)

*Exclusions:*

- 1) Non-English speaker or
- 2) Visually or hearing impaired

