These criteria were selected to ensure the focus and inclusion of YLH to fulfill the purpose and function of this proposed application for case management to serve this population, who most benefit from the support for care and services that the case management model provides. Additionally, our team wanted to ensure that the patients would be able to run the PlusCare app on their device for the needed length for the study.

The CM eligibility criteria are as follows:

*Inclusions:*

- 1) are actively employed BCH and
- 2) perform case management duties with HIV-positive patients 13-25 years old

**Description of Study Treatments or Exposures/Predictors:** Study participants will be given a username and access to the PlusCare app on their own personal devices. CMs will have access to the mobile app available on a study tablet that will be provided to each program or web app accessible from their own work computers.

**Definition of Primary and Secondary Outcomes/Endpoints:** Primary outcomes will be CD4 count, viral load, and HIV medical visit frequency. Secondary outcomes include emergency room visits and hospitalizations, adherence, patient reported quality of life, system usage data (such as log-ins) and system usability and satisfaction. This is detailed further in the table below:

Patient Measures	Pre	Post		Data Source
	1-year prior	Base	6-mos	
Baseline Demographics				
Current gender  , sexual orientation identity (BRFSS  ), age/date of birth, income & employment (STRIVE  ), years since diagnosis, time spent in case management, housing stability, insurance, retention and quality of care, treatment		x		Survey, EHR
Experience with Technology		x		Survey
Primary Outcomes				
CD4, viral load 	x	x	x	EHR (Lab data)
HIV medical visit frequency and gaps 	x	x	x	Billing data, EHR
Secondary Outcomes				
ED visits, hospitalizations	x	x	x	Billing data, Survey
Patient-centered: Quality of Life (CDC HRQOL-14), self-efficacy (based on chronic disease scale)	x	x	x	Survey
System: Usage (log in frequency, dwell time)		x		System data
System: Usability and Satisfaction 		x		Survey

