### **Statistical Analysis Plan**

The study analysis will follow an *intention-to-treat* approach to determine PlusCare's effect on outcomes related to HIV case management. Our primary outcomes will include Ryan White Program core performance measures (HIV viral suppression, HIV medical visit frequency, and gaps in medical visits). Secondary outcomes will include proximal outcomes (medication adherence), patient-centered outcomes (quality of life, self-efficacy), and system usage and usability. Usage data collected passively from the system from both patients and CMs will be analyzed to assess trends in system usage (e.g., what module was accessed by patients most frequently, how many documents were sent by CMs) and system usability will be assessed via the SUS administered at the end of the study. Baseline characteristics of our sample were summarized with descriptive statistics (mean, median, SD, frequency) and a Wilcoxon test for significance will be used to assess PlusCare's impact on our outcomes of interest pre- and post-intervention and a repeated measures analysis will be used to determine changes in outcomes assessed at each respective time point during pre- and post-intervention. Under the

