assumption that some individual specific effects are uncorrelated with the independent variables while some other effects are correlated, we will use mixed effects modeling to account for both time-variant and time-invariant factors. Initial cost-effectiveness analysis will be performed following methods used in previous studies. Data on HIV medical visit frequency and gaps and ED visits and hospitalizations will be used to perform this analysis. The monetary benefit from the PlusCare intervention arises from the cost savings as a result of reduction in hospital visit frequency between pre- and post-intervention. We will compute preliminary cost-effectiveness of the PlusCare intervention by comparing the cost savings attained with the program cost of the case management program using Net Present Value (NPV = *Present Value of Cost Savings – Present Value of Program Costs*) and the Return on Investment (ROI = *Present Value of Cost Savings / Present Value of Program Costs*). We hypothesize that the use of PlusCare will have a positive effect on the return on investment. All statistical analyses were performed using R statistical software (R Foundation for Statistical Computing, Vienna, Austria) or SAS software, version 9.2 (SAS Institute, Cary, NC) and a two-tailed P-value of the test < 0.05 was considered statistically significant.

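### Secondary outcomes can be declared significant at an unadjusted two-tailed 0.05, with no defined test set, hierarchy or exploratory label; the family-wise error is roughly 8–32%, depending on which outcomes are tested and how often.

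*Combined protocol and SAP*

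**What the plan says.** The last sentence of the Statistical Analysis Plan sets the only decision rule, and sets it for all statistical analyses: "a two-tailed P-value of the test < 0.05 was considered statistically significant".

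The same section assigns the tests. First, "a Wilcoxon test for significance will be used to assess PlusCare's impact on our outcomes of interest pre- and post-intervention". Second, "a repeated measures analysis will be used to determine changes in outcomes assessed at each respective time point during pre- and post-intervention". Both sentences come after the primary and secondary outcomes have been listed, and neither is limited to the primary ones. The outcomes of interest are not defined.

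The two lists of secondary outcomes differ:

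- Definition of Primary and Secondary Outcomes/Endpoints: "Secondary outcomes include emergency room visits and hospitalizations, adherence, patient reported quality of life, system usage data", followed by usability and satisfaction. Self-efficacy appears only in the table below that text.
- Statistical Analysis Plan: "Secondary outcomes will include proximal outcomes (medication adherence), patient-centered outcomes (quality of life, self-efficacy), and system usage and usability". ED visits and hospitalizations are absent here and return only as inputs to the cost-effectiveness analysis.

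No section gives a testing order, an alpha split, a multiplicity adjustment or an exploratory label for the secondary outcomes. Only the cost-effectiveness analysis is described as initial or preliminary.

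**The concern.** Under this rule the word secondary has no consequence. A secondary P of 0.04 is declared significant on the same terms as a primary one, whatever the primary outcomes show. Because the tested set is undefined and the two lists disagree, the family could also be settled after the data are seen.

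The stated objective is to "test and demonstrate the effectiveness of PlusCare on HIV case management process and care continuum outcome measures". In a study of 50 patients without a control group, the plan as written would let one isolated secondary P below 0.05 be called a significant effect of the app. The 5% error rate that the rule suggests applies to each test, not to the set.

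**Working it through.** **The plan's own figure.** The documents state no family-wise error rate for the secondary outcomes. The only stated rate is 0.05 per test. The 81% power figure concerns log10 viral load and does not bear on this point.

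**Step 1: which secondary outcomes can have a pre-post test.**

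| Outcome | Pre-intervention value described? | Counted |
|---|---|---|
| ED visits | Yes, outcome table | Yes |
| Hospitalizations | Yes, outcome table | Yes |
| Quality of life | Yes, outcome table | Yes |
| Self-efficacy | Yes, outcome table | Yes |
| Adherence | No: monthly item answered inside the app after enrollment; no row in the outcome table | No |
| System usage | No: it "will be analyzed to assess trends in system usage" | No |
| Usability | No: measured at the end of the study | No |

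Four outcomes remain. Only quality of life and self-efficacy are also on the Statistical Analysis Plan's own secondary list, so the narrowest reading has two.

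**Step 2: number of time points.** The follow-up assessment section gives 6 and 12 months, and the repeated measures analysis looks at each time point. So each outcome is tested once or twice.

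**Step 3: independent outcomes, by hand.** The chance of at least one P < 0.05 in k independent tests, when nothing changes, is 1 − (1 − 0.05)^k.

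- k = 2: 1 − 0.95² = 1 − 0.9025 = 9.8%
- k = 4: 1 − 0.95⁴ = 1 − 0.8145 = 18.5%

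**Step 4: correlated tests, by simulation.** The documents give no correlations, so these are assumptions: 0, 0.5 or 0.8 between outcomes and 0.5 between time points of one outcome, with the product for different outcomes at different times. Null multivariate normal test statistics were drawn (at least 400,000 per case), each tested two-sided at 0.05. Each outcome is one score tested by one method.

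| Tests | Correlation 0 | 0.5 | 0.8 |
|---|---|---|---|
| 2 outcomes, once each | 10% | 9% | 8% |
| 4 outcomes, once each | 19% | 16% | 11% |
| 4 outcomes, 6 and 12 months | 32% | 27% | 20% |

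Two outcomes tested at both time points give about 14–17%.

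**Step 5: effect of an adjustment.** Bonferroni over four tests uses 0.05 / 4 = 0.0125 each. With independent tests the family-wise rate is 1 − 0.9875⁴ = 4.9%, and less with positive correlation. Holm's procedure has the same rate when nothing changes and rejects at least as often otherwise.

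**The case against.** The strongest reply is that leaving secondary outcomes unadjusted in a small uncontrolled study is largely a reporting choice. The plan already separates primary from secondary outcomes, its only power calculation is for viral load, and no section says that one significant secondary result would establish effectiveness. That is fair as to weight. It does not supply the missing rule: the plan as written still declares every such P significant.

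Three stronger readings are tempting, and the documents do not support them.

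- A reader might infer that every secondary outcome is tested for impact. The plan says outcomes of interest, without defining them. Usage and usability cannot have a pre-post test.
- A reader might count adherence as a fifth outcome at two time points and reach about 31% at correlation 0.5. Adherence has no described pre-intervention value. The matching figure without it is about 27%.
- A reader might take these percentages as the risk of a false claim for an app that does nothing. They hold only if nothing changes over time. In a single-group pre-post design, regression to the mean or secular trend can produce significant changes without any effect of the app, and no multiplicity rule corrects that.

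It also stands that several primary outcomes share the same unadjusted 0.05. That is a separate gap, and a more serious one for an effectiveness claim; it is not assessed here.

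**Conclusion.** The concern holds in limited form. The plan applies an unadjusted two-tailed 0.05 to an undefined set of outcomes and gives the secondary ones no hierarchy, adjustment or exploratory label. With no change over time, the chance of at least one P below 0.05 is about 11–19% for the four pre-post outcomes tested once, about 20–32% if tested at 6 and 12 months, and about 8–10% on the narrowest reading. All exceed 5%.

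The sizes rest on assumed test counts and correlations, not on figures in the documents. Scoring quality of life as several components, or reading off both the Wilcoxon and the model results, would raise them.

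**What to change.** 1. In the last sentence of the Statistical Analysis Plan, limit the P < 0.05 declaration to the primary analysis.
2. Add: *Secondary outcomes are exploratory. They are reported as pre-post differences with 95% confidence intervals, and adherence as a trend over time. They are not used alone to claim effectiveness.*
3. Define the outcomes of interest, and name the same tested secondary set, with test and time point, in the outcome definitions, the table and the Statistical Analysis Plan.
4. If a confirmatory secondary claim is wanted, apply Holm's procedure at 0.05 across a named set of 12-month pre-post secondary outcomes, only after a significant primary analysis. The plan must then say which primary result opens that step.

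The cost is wording only, with no extra data or patients. The downside is that an isolated secondary P below 0.05 can no longer be called a significant effect of PlusCare. The change controls multiplicity only; any report should still say that the design cannot separate the app's effect from regression to the mean or secular trend.

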### **Statistical Power and Sample Considerations**

The power calculation was based on N=50 patients. With a confidence level of 95%, there is 81% power to detect a 38% change in log10 HIV viral load in patients pre- and post-intervention.

